Study Title	Reducing Binge Eating to Prevent Weight Gain in Black Women
Objectives	
Primary: Examine the feasibility and acceptability of a 6-month AAT + NUTR (N=48) intervention. AA women (BMI ≥ 25 kg/m²) with weekly binge eating episodes will be randomized to the AAT+NUTR (n=24) or wait-list control (n=24). The study will examine recruitment, retention, barriers to completion, satisfaction, and adherence.
 
Secondary: At 4 (end of treatment) and 6 months (follow-up), examine changes in (a) binge eating; (b) depressive symptoms; (c) dietary outcomes (e.g., overall energy intake, fat, fruit and vegetable intake); and (d) weight for participants in each group.
 
Tertiary/Exploratory: Conduct key informant interviews (n=15-20) with UNC Department of Family Medicine staff and participants to determine acceptability of the AAT intervention in the primary care setting.

Target Population	
Key Inclusion Criteria Individuals are eligible if they are non-Latino Black women, over 18 years of age, have a BMI ≥ 25kg/m², use a Bluetooth-enabled smartphone, report at least one binge eating episode weekly, and complete the screening.
 
Key Exclusion Criteria Individuals will be excluded if they are currently pregnant, in substance use treatment, involved in a weight loss program, have a history of anorexia nervosa, engage in purging, are currently receiving psychological or pharmacological treatment for disordered eating or eating disorders, or are concurrent intravenous drug users or consume >4 alcoholic beverages/day.

Numbers of Participants	
Number to be recruited for screening [some will not be eligible for enrollment] 200
 
Number of eligible participants enrolled [this is the target sample size for enrollment] 60

Clinical Phase	[I, II, III, or IV (if applicable)]

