Outcome Measures	
[Measures that will used to assess the intervention (for feasibility, tolerability, efficacy, safety, comparability, pharmacokinetics/pharmacodynamics, etc.)]
 
To assess the feasibility of recruiting adult, overweight/obese Black women to the proposed study, the percent of eligible overweight/obese black women who were enrolled and retained in the study will be examined and reasons for nonparticipation and attrition will be documented. Participants will also be asked to provide measurements for height/weight, blood pressure, binge eating, and complete several self-report measures.

Study Duration	2 years
Subject Participation Duration	30 hours
Estimated Time to Complete Enrollment	January 2019-July 2021
Statistical Analysis Plans	
[Feasibility will also be determined by calculation of point and interval estimates (95% confidence intervals using sample size methods) of the feasibility parameters (proportion/percentages in terms of eligibility, participation, retention; means/medians for attendance at intervention sessions) and bivariate frequency distributions. Linear mixed effects modeling will be used to predict the association between treatment group assignment (AAT + NUTR or control), and binge eating, dietary intake, and weight scores at T2 and T3. Baseline scores will be used as

	covariates in these analyses. Standardized mean differences (e.g., Cohen's d with bias adjustment) will also be calculated as an effect size measure with 95% CI.
--	---

2. Introduction: Background and Scientific Rationale

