5.4. Outcome Measures

Primary Outcome(s):

Table 2: Feasibility Measures (Aim #1) ³⁸	
Question of Interest	Feasibility Measures
Can we recruit our target population?	# of screened and eligible participants, and proportion of eligible screens who enroll
Will participants do what they are asked to do?	Adherence to study protocol (e.g. session attendance, homework completion)
Are the assessments too burdensome?	Proportion of planned assessments completed; duration of assessment visits
Will participants stay in the study?	% of study retention and reasons for dropouts
Is AAT + NUTR acceptable to study participants?	Semi-structured telephone interviews (n=15-20) will be conducted to receive feedback on intervention and suggestions for improvement.

Secondary Outcome(s): Linear mixed effects modeling will be used to examine the association between treatment group assignment (AAT + BWL or wait-list control group coded as a (0,1)-indicator) and binge eating, eating self-efficacy, depressive symptoms, weight, blood pressure, and waist circumference scores at 2 and 6 months.

6. Study Participants

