6.1. Number of Participants

Number to be recruited for screening: 160

Number of eligible participants enrolled: 60

Eligibility criteria includes Non-Latino Black women individuals over 18 years of age, have a BMI ≥ 25 kg/m², use a Bluetooth-enabled smartphone, and report at least one binge eating episode weekly. We will recruit participants in two ways: 1) We will request an IRB-waiver to allow [name], the director of the Weight Management Program and co-investigator on this study to a list of eligible participants (e.g., Non-Hispanic, AA & White women, BMI > 30 kg/m²) at UNC Family Medicine. The names will be randomly ordered, and women will be sent an introductory letter via email and/or postal mail describing the project and inviting them to contact the research team if no further contact is desired. If no such contact is received, the letter will be followed by a telephone call from the project coordinator, who will discuss all components of informed consent and participation. 2) Potential participants will respond to flyers, email announcements in community centers, doctor's offices, churches, and university listservs. Participants will also be approached in local community agencies by community center staff members and lay health counselors to request their consent to be approached by a member of the research team. IRB-approved flyers will be posted in the lobbies and recreation halls of the community facilities. Potential participants may self-refer to the study after reading the flyer.

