9.1. Outcome Measures for Evaluation of Feasibility / Tolerability

To assess the feasibility of recruiting adult, AA women to the proposed study, the percent of eligible women who were enrolled and retained in the study will be examined and reasons for nonparticipation and attrition will be documented. Feasibility will also be determined by calculation of point and interval estimates (95% confidence intervals using sample size methods) of the feasibility parameters (proportion/percentages in terms of eligibility, participation, retention; means/medians for attendance at intervention sessions) and bivariate frequency distributions.

Question of Interest	Feasibility Measures
Can we recruit our target population?	# of screened and eligible participants, and proportion of eligible screens who enroll
Will participants do what they are asked to do?	Adherence to study protocol (e.g. session attendance, homework completion)
Are the assessments too burdensome?	Proportion of planned assessments completed; duration of assessment visits
Will participants stay in the study?	% of study retention and reasons for dropouts
Is AAT + NUTR acceptable to study participants?	Semi-structured telephone interviews (n=15-20) will be conducted to receive feedback on intervention and suggestions for improvement.

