10.2. Description of the Study Cohort

Descriptive analyses will first be performed overall, by treatment group, and time points to identify any data anomalies (e.g., missing data, outliers, non-normality) that may invalidate study findings. Remedial measures (e.g., single/multiple imputation of missing data, score/data transformation) will be applied as indicated based on the results of data screening.

² [1] www.consort-statement.org; [2] www.strobe-statement.org; [3] www.icmje.org; [4] Wasserstein RL, et al. (2016), The ASA's Statement on p-Values, *The American Statistician*, 70:2, 129-133. [5] Wasserstein RL, et al. (2019), Moving to a World Beyond $p < 0.05$, *The American Statistician*, 73:sup1, 1-19. [6] Amrhein, et al. (2019) Scientists rise up against statistical significance, *Nature* 567, 305-307. [7] Editorial (2019) It's time to talk about ditching statistical significance: Looking beyond a much used and abused measure would make science harder, but better. *Nature* 567, 283-283.

10.3.Aim-Specific Plans

Plans for Aim 1: [e.g., to evaluate Efficacy, characterize and compare two treatment regimens]

To evaluate the feasibility and acceptability of 6-month AAT + NUTR, we will examine several feasibility outcomes. To assess the feasibility of recruiting adult, AA women to the proposed study, the percent of eligible women who were enrolled and retained in the study will be examined and reasons for nonparticipation and attrition will be documented. Feasibility will also be determined by calculation of point and interval estimates (95% confidence intervals using sample size methods) of the feasibility parameters (proportion/percentages in terms of eligibility, participation, retention; means/medians for attendance at intervention sessions) and bivariate frequency distributions.

Plans for Aim 2: [e.g., to evaluate Safety, characterize and compare two treatment regimens]

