10.6. Sample Size Rationale

Because this is a feasibility study, we are not prioritizing powering the sample to determine the efficacy of the AAT intervention. However, we ran conservative tests for statistical power incorporating parameters from our preliminary study using G*Power. Based on our analysis, we determined that a sample of 60, evenly allocated between treated and control groups, is sufficiently powered (.80) to identify large standardized mean differences in binge eating ($d = .74$) (Aim #2). The sample, however, is underpowered to determine differences in weight. Because this study is exploratory, we are prioritizing feasibility, and an exploration of differences, rather than determining efficacy. This is a pilot study, If this pilot study is successful, we will conduct a larger study with a greater sample of participants and test the AAT intervention for a longer duration.

11. Safety Monitoring and Management

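### A larger study depends on the pilot succeeding, but no criterion for success is set, and the recruitment targets that might supply one contradict each other

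*Combined protocol and SAP*

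**What the plan says.** The Synopsis and Section 3.1 make feasibility and acceptability the primary objective, covering recruitment, retention, barriers, satisfaction and adherence. Section 10.6 then looks ahead: "If this pilot study is successful, we will conduct a larger study with a greater sample of participants".

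The Aim 1 plan in Section 10.3, which largely repeats Section 9.1, has two parts. First, "the percent of eligible women who were enrolled and retained in the study will be examined and reasons for nonparticipation and attrition will be documented". Second, "Feasibility will also be determined by calculation of point and interval estimates (95% confidence intervals using sample size methods) of the feasibility parameters". The feasibility table in Sections 5.4 and 9.1 asks plain questions, such as whether participants will stay in the study, and answers each with a measure (for retention, the percentage "of study retention and reasons for dropouts") but no target. It also lists 15 to 20 interviews on acceptability.

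The planned recruitment figures are:

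- **Screening.** The Synopsis has "Number to be recruited for screening [some will not be eligible for enrollment] 200"; Section 6.1 has "Number to be recruited for screening: 160".
- **Enrolment.** 60 in the Synopsis (numbers of participants) and Sections 2.3, 5, 5.2, 6.1 and 10.6; 48, as 24 per arm, in the Synopsis (objectives) and Sections 3.1 and 5.1.
- **Timing.** The Synopsis gives enrolment as "January 2019-July 2021" and the study duration as 2 years. The last assessment is at month 6.

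**The concern.** An estimate and its interval describe what happened. They do not say whether it was good enough unless a reference value was fixed beforehand. Here a decision of consequence, whether to run a larger trial, is tied to success, and the reference value is missing. If month 6 retention came out at 70%, one reader could call the pilot a success and another could not, and both would be consistent with the protocol.

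Section 10.1 undertakes that the plan for each aim will be finalized before data collection and will set out the steps for inference as well as estimation. Aim 1 has the estimation step only.

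The natural fallback would be to ask whether the trial recruited as planned. That question has no single answer either, because the number to enrol, the number to screen and the time allowed each take more than one value.

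**Working it through.** **1. Is there a criterion anywhere?** The places where one could stand, set side by side:

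| Place | Content | Numeric criterion |
|---|---|---|
| 5.4 and 9.1, feasibility table | Measures for recruitment, adherence, burden, retention; interviews | None |
| 9.1 and 10.3, Aim 1 | Estimates, 95% intervals, documented reasons | None |
| 10.6 | Larger study if the pilot succeeds | None |
| 11.5 and 12.2 | Compliance, attrition, futility as possible grounds for stopping | None |
| 2.2 | 88% retention in an earlier pilot (n=31) | Background only; not adopted as a target |

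**2. The plan's own power figure.** Section 10.6 claims power 0.80 for 60 women, evenly allocated, at d = 0.74. A two-sample t-test at two-sided 0.05 (alpha and sidedness are not stated, so this is assumed) with 30 per arm gives 0.805, so the figure reproduces. It concerns Aim 2 and supplies no feasibility criterion. With 24 per arm the same calculation gives 0.709, so the choice between 48 and 60 matters beyond Aim 1.

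**3. Can 48 be the expected completers out of 60?** 48/60 = 80%, which would be a plausible completion rate. But Sections 3.1 and 5.1 say that the 48 will be randomized, so the two numbers describe the same event and conflict.

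**4. Timing.** January 2019 to July 2021 inclusive is 12 + 12 + 7 = 31 months. A 2-year study with a month 6 assessment leaves at most 24 − 6 = 18 months for enrolment, before any allowance for start-up or analysis. Required accrual = number enrolled / months:

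| Enrolled | Over 31 months | Over 18 months |
|---|---|---|
| 60 | 60/31 = 1.9 per month | 60/18 = 3.3 per month |
| 48 | 48/31 = 1.5 per month | 48/18 = 2.7 per month |

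The 18-month rates are minima. An accrual of, say, 2.5 per month would be ahead of plan on one reading and behind on the other.

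**5. Do the intervals settle the matter?** Exact (Clopper-Pearson) 95% intervals for retention out of 60: 42/60 = 70%, 57% to 81%; 48/60 = 80%, 68% to 89%; 53/60 = 88%, 77% to 95%. Neighbouring results overlap widely, so computing the interval does not replace a rule.

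**6. Would a rule discriminate at this size?** Take an illustrative go at observed retention of 80% or more (at least 48 of 60, or 39 of 48) and stop below 65% (38 or fewer of 60, or 31 or fewer of 48). These cut-offs are assumptions and are not in the documents. Binomial probabilities:

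| True retention | Go, N=60 | Go, N=48 |
|---|---|---|
| 70% | 0.06 | 0.06 |
| 80% | 0.58 | 0.50 |
| 88% | 0.98 | 0.94 |

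Stop has probability 0.74 (N=60) or 0.79 (N=48) at true retention of 60%, and below 0.01 at 80%. The rule separates 70% from 88% well. It is close to a coin toss at 80%, which is what a cut-off at the true value must give.

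**The case against.** The strongest reply is that this is an exploratory pilot whose stated objective is to examine feasibility, and that estimates with intervals do exactly that. On this view the sentence about a larger study is a closing remark on future work, not a formal progression gate. Much of this stands. A reader might infer that the primary question has no answer under the plan, or that feasibility rests on computed estimates alone. The documents do not support either: the objective is descriptive and will be described, and the plan also documents reasons for non-participation and attrition and holds interviews. Nor does it follow that any result whatever could be presented as success, since Sections 11.5 and 12.2 recognise compliance and attrition problems as possible grounds for stopping, though without numbers. What remains is that the protocol itself makes the next study conditional on success and leaves success to be decided afterwards.

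It is also tempting to treat 60/200 = 30% against 60/160 = 37.5% as two rival recruitment benchmarks. That goes too far. The protocol's proportion is enrolled per eligible screen, while 200 and 160 count everyone recruited for screening, including women who prove ineligible. No expected eligible count is given. The conflict therefore bears on the count to be screened and not on that proportion, and a confidence interval around a planned ratio would mean nothing.

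Finally, the 88% from the earlier pilot is a weak comparator. It came from a study of AAT alone in 31 women, with its binge-eating result reported at 8 weeks; here retention runs to month 6 after 16 weeks of AAT and nutrition sessions. It can inform a cut-off but should not be adopted as one.

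**Conclusion.** The point holds and should be acted on. No criterion for success appears in the text supplied, so the judgement that leads to a larger study would be made with the data in hand. The planning figures cannot stand in for a criterion: screening is 200 or 160, enrolment 60 or 48, and the enrolment window exceeds the whole study by 7 months (31 against 24). Required accrual is about 1.9 per month for 60 women over the stated window, and at least 2.7 to 3.3 per month if follow-up is to finish within two years.

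The finding does not touch participant safety or the validity of the Aim 2 estimates. It rests on reading the 2-year duration as including the month 6 follow-up of the last participant, and on no progression criterion standing in pages that were not available.

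**What to change.** 1. State one screening target, one enrolment and randomization target, and one enrolment window that fits the study duration with 6 months of follow-up, and use them in the Synopsis and in Sections 2.3, 3, 5, 6.1 and 10.6. If 48 is the intended number, redo the power statement.
2. Add to Section 10.3, before enrolment starts, a go / amend / stop rule for month 6 retention, for the number enrolled against the corrected target within the window, and for sessions attended out of 16. Say for each whether the point estimate or a confidence bound is judged, and how the measures combine.
3. Make the bands contiguous. For retention, an illustration is go at 80% or more, amend from 65% to below 80%, stop below 65%. Bands written in whole percentages (65 to 79, then 80) would leave 38/48 = 79.2% unclassified. The sponsor sets the cut-offs; what matters is that they are fixed in advance.
4. If enrolled per eligible screen is to be a criterion, first give the expected number of eligible women.

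The cost is protocol wording, with no added participants or visits. The real price is that the sponsor commits in advance to a result that would count against proceeding, and near any cut-off the outcome will depend partly on chance.

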11.1. Risk / Benefit Assessment

Potential Risks:

The major risks are likely to be fatigue, distress from revealing personal information and possibly during the intervention trial if the participant is not feeling like she is making progress. If participants complain about fatigue or distress, they will be given an opportunity to complete the questionnaire later.

Potential Benefits: [State anticipated direct benefit(s) for individual subjects, if any, or to society]

Participants may benefit from the tools learned within the intervention, and healthy non-eating coping skills. Study participants will also have the opportunity to receive support from sharing of their experiences and may receive further insight regarding tools to manage their binge eating behaviors and gain awareness for future weight loss attempts. They may also experience pride in knowing that they are contributing to a study that may make a significant contribution to the field in the future.

11.2. Assessment of Safety

To minimize emotional distress, if participants cite this concern, they will be provided the option to a) pause

and regroup; and/or b) finish the survey at a later time. If the previous is not sufficient, and participants report experiencing significant distress, participants will be provided the number to Hopeline (<https://www.hopeline-nc.org>; [contact]), a North Carolina crisis line and to the local emergency room.

Participants who experience significant distress will also be asked permission to provide their contact information to the PI ([name]). [name], who is a licensed clinical social worker, will contact those

participants on the next day. [name] will also be updated immediately on all participants who experience

significant distress.

Depression – Beck Depression Inventory

Using the total score (from all added scores on the BDI), the following interpretation applies:

Total Score	Range of Depression
0 – 13	Minimal
14 – 19	Mild
20 – 28	Moderate
29 – 63	Severe

Potential participants who on initial assessment (or is there a screening assessment) have a BDI-II score of 29 or greater (“severe” depression) are excluded from the study (please see below).

If a participant’s total score is 20 or greater, this will be reported to the Principal Investigator (PI) or Project Director (PD) who will discuss their results, inquire about current status and

treatment, will **provide information on community resources for the treatment of depression, and document the conversation and actions taken.**

For question #9 “Suicidal Thoughts or Wishes”: If a participant chooses response option 1, 2 or 3, this will be reported to the PI or PD who will discuss the results, inquire about current status and treatment and document the conversation and actions taken (providing a detailed note of the discussion that will be maintained using the participant’s ID number). The participant will also be referred to their PCP, given a list of mental health providers in the community, and urged to seek treatment if they are not already receiving treatment.

If a participant endorses suicidality or imminent fear of self-harm, the PD will contact and inform the PI (who is a licensed mental health professional), and also make telephone contact with the local suicide crisis network while in the presence of the participant; if a significant other is with the participant, that individual will be provided with instructions to accompany the person to the nearest Emergency Room. In either of these situations, the individual will be asked for permission to contact and inform their PCP of their condition.

11.3.Unanticipated Problems, Adverse Events, Serious Adverse Events

Unanticipated Problems: An unanticipated problem is any incident, experience or outcome that meets all three OHRP criteria (1) unexpected (in severity, specificity, frequency, or nature), (2) related or possibly related to the research, and (3) suggests the research places subjects or others at greater risk than previously known or recognized.

Adverse Event (AE) Definitions: An adverse event is one that occurs during the course of a research protocol that either causes physical or psychological harm, or increases the risk of physical or psychological harm, or results in a loss of privacy and/or confidentiality to a research participant or others (such as family members).

Serious Adverse Events (SAE) Definition: A serious adverse event means any event temporally associated with the subject's participation in research that meets any of the following criteria: results in death; is life threatening (places the subject at immediate risk of death from the event it occurred); requires inpatient hospitalization or prolongation of existing hospitalization; results in a persistent or significant disability/incapacity; results in a congenital anomaly/birth defect; or any other adverse event that, based upon appropriate medical judgement, may jeopardize the subject's health and may require medical or surgical intervention to prevent one of the outcomes listed .

Reporting and Documentation Procedures:

Data and safety monitoring will be conducted during meetings with the PI and research assistants during which recruitment, data acquisition, management and any adverse events arising from the study will be reviewed. Any unanticipated and adverse events will be reported immediately to the IRB, a serious event will be reported to the IRB and funding agency.

Participant Notification of New Information: All participants will be aware of new safety information within 7 days of the event preceding the development of new information.

11.4.Safety Monitoring

Data and safety monitoring will be conducted during meetings with the PI and research assistants during which recruitment, data acquisition, management and any adverse events arising from the study will be reviewed. Any unanticipated and adverse events will be reported immediately to the IRB, a serious event will be reported to the IRB and funding agency.

11.5.Study Suspension / Early Termination of the Study

Given that this is such a minimal risk intervention, we do not expect that serious AEs will occur and require stopping the trial. Though extremely unlikely, difficulties with compliance and/or attrition would be far more likely to result in trial stoppage. However, as previously noted, we, along with our safety officer, will closely monitor any injury rates and notify the UNC Chapel Hill IRB and the UNC NORC if a larger than expected SAE rate is observed.

12. Supporting Documentation and Operational Considerations

12.1.Regulatory, Ethical, and Study Oversight Considerations

The following subsections should include a description of the regulatory and ethical considerations, and context for the conduct of the trial. Of note, the guiding ethical principles being followed by this study are included in the **Statement of Compliance** at the beginning of this protocol. For NIH Intramural Research Program studies only: A statement referencing compliance with NIH Human Research

Protections Program policies and procedures is adequate for **Subsection 10.1.1, Informed Consent Process.**

